4. **Statistical Methods:**

Primary - Analysis of covariance (ANCOVA) with “type of surgery” as a covariate will be used to compare mean ME between the two groups. (The inclusion of these covariates in the model is in accordance with ICH E9 Section 5.7 guidelines.) Data transformation (presumably a log transform) will be considered in order to achieve the required assumptions of normality and equal variance.

Secondary – The chi-square test will be used to compare anti-emetic rates and patient satisfaction. ANCOVA will be used to compare LOS, pain and nausea scores.

5. **Intention to Treat (ITT):** The ITT population will be defined as all subjects who are randomized. All primary analyses will be carried out on the ITT population.
6. **Sample Size Considerations:** A two-sample t-test approach is used as a reasonable simplification of the ANCOVA method. Based on previous data, it is expected that the Placebo group will average 12 ME (SD=4) of narcotics in the PACU. A reduction of 20% to 9.6 ME in the Bipuvacaine group would be clinically significant. A sample size of n=45 subjects per group (total 90) will yield 80% power to detect such a reduction (alpha=0.05, 2-tailed t-test).
7. **Interim Analysis:** There will be no interim analysis for early stopping of the trial.

j. Adverse events

An adverse event (AE) is any untoward medical occurrence in a clinical investigation of a patient administered a pharmaceutical product and that does not necessarily have a causal relationship with the treatment. An AE therefore is any unfavorable and unintended sign (including an abnormal laboratory finding), symptom or disease temporally associated with the administration of an investigational product, whether or not related to the investigational product. An unexpected AE is one of a type not identified in nature,

severity, or frequency in the study protocol or of greater severity or frequency than expected based on the information in the study protocol.

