AEs will be reported in the patient's medical record and reviewed by the PI, who records, reviews, evaluates, and manages all AEs. Any unanticipated problems which occur will be primarily addressed by the principal investigator and other physician investigators. Serious AND Unanticipated AND possibly, probably or definitely related AEs will be reported to the IRB as per their specific reporting requirements. Modifications to the protocol, if required, will be determined by the PI in cooperation with the IRB. Abnormal results of diagnostic procedures are considered to be AEs if the event:

- results in study withdrawal
- is associated with a serious adverse event
- is associated with clinical signs or symptoms
- leads to additional treatment or to further diagnostic tests
- is considered by the investigator to be of clinical significance

Adverse events will be classified as serious or non-serious. A ***serious adverse event*** is any AE that is:

- fatal
- life-threatening
- requires or prolongs hospital stay
- results in persistent or significant disability or incapacity
- a congenital anomaly or birth defect
- an important medical event

Important medical events will be defined as those that may not be immediately life threatening, but are clearly of major clinical significance. They may jeopardize the subject, and may require intervention to prevent one of the other serious outcomes noted above. All adverse events that do not meet any of the criteria for serious will be regarded as ***non-serious adverse events***.

1. *Preexisting Condition*

A preexisting condition is one that is present at the start of the study. A preexisting condition will be recorded as an adverse event if the frequency, intensity, or the character of the condition worsens during the study period.

2. *General Physical Examination Findings*

At screening in pre-surgical testing, any clinically significant abnormality will be recorded as a preexisting condition. At the end of the study, any new clinically significant findings/abnormalities that meet the definition of an adverse event must also be recorded and documented as an adverse event.

3. *Post-study Adverse Event*

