All unresolved adverse events will be followed by the investigator until the events are resolved, the subject is lost to follow-up, or the adverse event is otherwise explained. The investigator will instruct each subject to report any subsequent event(s) that the subject, or the subject's personal physician, believes might reasonably be related to participation in this study. The investigator will notify the IRB of any death or adverse event occurring at any time after a subject has discontinued or terminated study participation that may reasonably be related to this study.

Abnormal Laboratory Values

A clinical laboratory abnormality will be documented as an adverse event if any one of the following conditions is met:

- The laboratory abnormality is not otherwise refuted by a repeat test to confirm the abnormality
- The abnormality suggests a disease and/or organ toxicity
- The abnormality is of a degree that requires active management; e.g. change of dose, discontinuation of the drug, more frequent follow-up assessments, further diagnostic investigation, etc.

4. *Hospitalization, Prolonged Hospitalization or Surgery*

Any adverse event that results in hospitalization or prolonged hospitalization will be documented and reported as a serious adverse event unless specifically instructed otherwise in this protocol. Any condition responsible for surgery should be documented as an adverse event if the condition meets the criteria for an adverse event. The condition, hospitalization, prolonged hospitalization, or surgery will be reported as an adverse event in the following circumstances:

- Hospitalization or prolonged hospitalization for diagnostic or elective surgical procedures for a preexisting condition. Surgery will **not** be reported as an outcome of an adverse event if the purpose of the surgery was elective or diagnostic and the outcome was uneventful.
- Hospitalization or prolonged hospitalization required to allow efficacy measurement for the study.
- Hospitalization or prolonged hospitalization for therapy of the target disease of the study, unless it is a worsening or increase in frequency of hospital admissions as judged by the clinical investigator.

k. Recording of Adverse Events

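### The lead-in to the hospitalization list in 9.j.4 says the listed stays will be reported as adverse events, which is inconsistent with its own bullets and with the adverse event definition in 9.j

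*Combined protocol and SAP*

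**What the plan says.** All of this stands in section 9.j of the combined protocol and SAP, mostly in item 4 on hospitalization.

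- **Opening sentence of 9.j.4.** An adverse event that leads to or prolongs hospitalization "will be documented and reported as a serious adverse event unless specifically instructed otherwise in this protocol".
- **Lead-in to the list.** "The condition, hospitalization, prolonged hospitalization, or surgery will be reported as an adverse event in the following circumstances". Three bullets follow.
- **Bullet 1.** "Hospitalization or prolonged hospitalization for diagnostic or elective surgical procedures for a preexisting condition". A second sentence adds that uneventful elective or diagnostic surgery is not to be reported as the outcome of an adverse event.
- **Bullet 2.** "Hospitalization or prolonged hospitalization required to allow efficacy measurement for the study".
- **Bullet 3.** A stay to treat the study's target disease, "unless it is a worsening or increase in frequency of hospital admissions as judged by the clinical investigator".

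The rules that the list should agree with are:

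- **Definition, start of 9.j.** "An adverse event (AE) is any untoward medical occurrence in a clinical investigation of a patient administered a pharmaceutical product". The definition goes on to describe such a sign, symptom or disease as unfavorable and unintended.
- **9.j.1.** "A preexisting condition will be recorded as an adverse event if the frequency, intensity, or the character of the condition worsens".
- **Seriousness criteria in 9.j.** One criterion is that the event "requires or prolongs hospital stay".

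**The concern.** The lead-in is an operative reporting rule. Followed literally, it makes adverse events out of stays in which nothing untoward has happened. In bullet 3 it lists the unremarkable case and leaves out the worsening case.

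What is at stake is classification. A stay reported under the lead-in could then be counted as serious, because needing or prolonging a hospital stay is a seriousness criterion. Under 9.o it would go at once to the PI, the co-investigators and the Medical Monitor. Under 9.l it would go to the IRB according to that board's policies. Section 9.o also has the monitoring assess the number and type of serious adverse events, so such a stay would enter that count. A person working from the lead-in and a person working from the definition could classify the same stay differently.

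**Working it through.** No figure in the plan bears on this point, so the check sets the passages side by side.

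**Step 1: bullet 2 against the definition.** A stay arranged so that efficacy can be measured is planned by the study. It is neither untoward nor unintended. The lead-in makes it an adverse event and the definition does not.

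**Step 2: bullet 1 against the definition and 9.j.1.** A stay for an elective or diagnostic procedure for an unchanged preexisting condition is not untoward either. If the condition has worsened, 9.j.1 already requires an adverse event, so the only cases that bullet 1 adds are the unchanged ones. In 9.j.1 worsening is the trigger for recording, and those cases lack it. The second sentence of bullet 1 helps only in part: it exempts uneventful elective surgery, but not the stay itself. It would sit more naturally in a list of exclusions.

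**Step 3: bullet 3 under each possible lead-in.** The exception removes the worsening case from whatever the lead-in states.

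| Lead-in | No worsening | Worsening |
|---|---|---|
| As written (will be reported) | adverse event | not on the reporting list |
| Negative (will not be reported) | not an adverse event | adverse event |

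Only the second row gives the exception a sensible purpose and agrees with the definition. It also matches the logic of 9.j.1, though only by analogy: 9.j.1 concerns conditions present at the start of the study, and the protocol does not define the target disease.

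**Step 4: does other text correct the lead-in?** None does. The opening sentence of 9.j.4 expects exceptions to be stated somewhere in the protocol. This list is the natural place for them, but as worded it supplies none. The sentence is complete, and nothing suggests a redaction or a fault in text extraction.

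**Step 5: are true events lost?** No. The list does not claim to be exhaustive. The opening sentence of 9.j.4, the rules earlier in 9.j, and the requirement in 9.k to record every adverse event in the study period all still apply. The error therefore runs toward over-reporting.

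**Step 6: how many stays?** The documents give no rate, so no count is estimated. Section 8.b requires outpatient surgery, and under 9.g the last scheduled contact is within one week of surgery, which leaves little time for an elective admission. No section calls for a stay to measure efficacy, so bullet 2 probably has no cases. The number need not be zero, since 9.h does provide for recording narcotic and antiemetic use during a hospital stay.

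**The case against.** **The literal text can be followed.** Under bullet 3, an unchanged target-disease stay would be an adverse event through the list, and a worsening that led to hospitalization would be a serious adverse event through the opening sentence of 9.j.4. This is true, and it is why no event need be lost. But it makes a stay with nothing untoward reportable, against the definition, and it leaves the exception without a purpose. The inconsistency remains.

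**The comparison with 9.j.1 does not govern bullet 3.** This stands. Section 9.i.1 describes the trial as one of treatment for post-operative pain. If that is the target disease, it is not present at the start of the study. The firm ground is the definition for bullets 1 and 2, 9.j.1 for bullet 1, and the internal logic of bullet 3.

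**Review limits the harm.** This stands as well. The Study Summary describes a single-center trial, and under 9.j the PI reviews and evaluates every adverse event. Under 9.o the Medical Monitor then reviews all of them for relatedness and severity. An elective stay should be recognized at one of these steps.

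**Making the lead-in negative is riskier than leaving it.** On its own, it could be. The opening sentence of 9.j.4 gives way wherever the protocol instructs otherwise, so a bare negative could exempt a stay prolonged by post-operative pain if pain is taken as the target disease. This is a reason to make the companion changes at the same time, not to keep the present text.

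**Stronger readings.** A reader might infer that worsening events will go unreported, or that the safety conclusions or a decision to stop the trial could be distorted. The documents do not support either. The other rules in 9.j and 9.k still capture a worsening, and the stopping rules in 9.n contain no numerical threshold that an extra event could cross.

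**Conclusion.** The lead-in of 9.j.4 is inconsistent with its own bullets and with the adverse event definition, and for bullet 1 with 9.j.1 too. This is an internal inconsistency of minor severity. Its likely effect is a possible few over-reported or inconsistently classified stays in the adverse event and serious adverse event listings. The narcotic-use endpoint, the sample size and every other efficacy analysis are untouched.

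The conclusion that the list contradicts other text rests on the wording alone. That the list was meant to state exclusions is an inference, drawn from the exception in bullet 3, the second sentence of bullet 1 and the opening sentence of 9.j.4. The judgment that cases will be few rests on the outpatient setting and the short follow-up, not on any rate in the documents.

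**What to change.** Reconcile the list with the definition in 9.j and with 9.j.1 by three changes in one amendment:

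1. Make the lead-in negative by inserting *NOT* after *will*, so that the bullets become circumstances in which no adverse event is reported.
2. Add a sentence stating that any stay caused or prolonged by an event that meets the adverse event definition is still reported as a serious adverse event.
3. Define the target disease, or delete bullet 3.

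The first change should not be made without the other two, because alone it could replace over-reporting with under-reporting. The cost is one inserted word, one sentence, and one definition or deletion, with IRB review of the amendment. It adds no patients, visits or data.

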10. DATA HANDLING AND RECORD KEEPING

Any paper documents that contain PHI (e.g., link between the ID to subjects' identifiers) will be stored in a locked cabinet within the anesthesiology research office, separately from any de-identified research documents. IRB-approved personnel will be the only individuals with access to any research documents containing PHI.

Any electronic documents that contain PHI will be stored on REDCap. The Feinstein Institute for Medical Research will be used as a central location for data processing and management. Vanderbilt University, with collaboration from a consortium of institutional partners, has developed a software toolset and workflow methodology for electronic collection and management of research and clinical trial data. REDCap (Research Electronic Data Capture) data collection projects rely on a thorough study-specific data dictionary defined in an iterative self-documenting process by all members of the research team with planning assistance from the Biostatistics Unit of the Feinstein Institute for Medical Research. The iterative development and testing process results in a well-planned data collection strategy for individual studies. REDCap servers are housed in a local data center at the Feinstein and all web-based information transmission is encrypted. REDCap was developed specifically around HIPAA-Security guidelines and is recommended to Northwell Health researchers by both our Clinical Research Service, Research Compliance Office and Institutional Review Board. REDCap has been disseminated for use locally at other institutions and currently supports 1,244 active institutional partners and other institutions in 87 countries (www.project-redcap.org).

No PHI or research data will be stored on any Portable Electronic Devices (e.g., laptops, tablets, flash drives, etc.).

Any research data that will be emailed will be de-identified and encrypted. PHI will not be emailed to any commercial email addresses (e.g., Gmail, Yahoo, Hotmail).

Data safety will be monitored on an ongoing basis by the PI and in the event that a problem occurs, the problem will be managed by the PI and reported to the IRB according to requirements

11. DATA DISCLOSURE/PUBLICATION

Investigators intend to publish the results of this study. Any published results will only include an aggregate of de-identified data. No protected health information will be disclosed outside of Northwell Health for the purposes of this research.

Protected health information may be shared with:

- The Institutional Review Board (IRB) at Northwell Health;
- Doctors and staff at the hospital where this research study will take place;
- Doctors and staff at other institutions that are participating in the research study;
- Data and Safety Monitor(s), independent expert(s) that review the information from this research throughout the study; and/or
- Governmental entities that have the right to see or review your protected health information, such as the U.S. Office of Human Research Protections and the FDA.

Protected health information will only be used and/or given to others to perform this research; to study the results; and to determine if the research was done correctly. All reasonable efforts will be made to maintain confidentiality (in accordance with the measures outlined above).

13. CONFLICT OF INTEREST

The investigators have no conflicts of interest to report.

